6. HUMAN SUBJECTS RESEARCH CONSIDERATIONS

6.A. Risks to Study Subjects

6.A1. Involvement of Subjects

Subjects will be recruited into this study at the time that biliary atresia is suspected and exploratory surgery is scheduled or within 72 hours following portoenterostomy. Subjects will be randomized to treatment with corticosteroids or placebo treatment for 13 weeks and followed as outpatients until age 24 months.

6.A2. Planned Duration of the Entire Study

Based on the anticipated enrollment of 40-50 subjects/year by all ChiLDREN centers, we estimate completing enrollment within 3-4 years, with an additional 6 months to gather follow-up data on subjects enrolled in the final year. However, the testing of secondary outcome measures (such as survival with native liver at 24 months of age) and the careful monitoring of potential long-term adverse effects of corticosteroids (such as administration of developmental tests to screen for impaired neurodevelopmental outcome at 1 and 2 years of age) will extend the overall duration of the study to 6 years.

6.A3. Duration of Participation for Each Subject

Each subject will remain in the clinical trial until 24 months of age; i.e, for between 18 and 24 months. The use of corticosteroids will be limited to 13 weeks. This will be followed by very close follow-up in outpatient clinics until 12 months of age, followed by outpatient visits at 18 and 24 months of age. Subjects will be seen clinically as needed (by either their primary care provider or by a gastroenterologist at the study site) for evaluation and management of medical problems that may arise because of the natural progression of liver disease in affected children.

6.A4. Sources of Research Material

Subjects will be recruited from the pool of infants with jaundice referred to or evaluated by the outpatient and inpatient services at the ChiLDREN clinical centers. Research material will include clinical and laboratory data, physical findings, and data collected as part of the prospective observational database.

6.A5. Potential Risks to Subjects

There are two potential sets of risks associated with this clinical trial. The first set derives from the time of blood draws, and includes amount of blood, as well as pain, bruising, or superficial phlebitis. Most of the scheduled venipunctures, except that at the two-week follow up visit, are part of routine tests necessary for the proper care of infants following portoenterostomy; serum levels of electrolytes and glucose will be included to monitor for possible adverse effects of corticosteroid treatment. Only the blood draw at the two-week follow up visit to monitor for side effects is added by this study.

6.A5a. Amount of Blood

Blood is drawn as part of the routine clinical care of the subject, to be sent the repositories as part of the prospective database, and to monitor for vitamin levels and adverse events in this clinical trial. The cumulative amount of blood to be drawn is outlined in Tables 10 and 11 below.

Blood drawn for the ChiLDREN Prospective Observational Database:

Table 10. Amount of blood drawn from infants *to be sent to the repositories as part of the prospective observational database.*

Visit	Amount in ml drawn for research at the visit	Maximum research blood draw in ml within 2-month period	Maximum research blood draw in ml within 3-month period
Initial	4	4	4
4 weeks post op or post diagnosis	4	8	8
3 months post op or post diagnosis	4	8	12*
6 months post op or post diagnosis	4**	8 or 9.2	8 or 9.2
12 months of age	9.2	9.2	9.2
18 months of age	4	4	4
Annually from age 2	4	4	4

* This would only happen if the 3-month post-op or post-diagnosis visit was scheduled before the 3-month anniversary of the operation or diagnosis.

** When the 6 month post-op or post-diagnosis visit is at 10 months of age or greater, the blood draw at that visit will be that for 12 months of age and there will be no blood draw at 12 months of age.

NOTE: Blood volume for clinically indicated tests: Approximately, 6.5 ml of blood may be removed from the child at each visit to evaluate hepatic function, electrolytes and differential. More may be withdrawn to perform additional clinically indicated lab tests.

Additional blood drawn to monitor for vitamin levels and adverse events for this clinical trial:

At each follow up visit, 1 ml of blood will be drawn to monitor serum electrolytes and glucose which may not be drawn as part of standard clinical care.

At follow-up visits (4 weeks post surgery, 3 and 6 months post, and at 12 mo, 18 mo, and 24 mo of age, 6-9 ml of blood will be drawn to monitor vitamin levels, total bile acids and PIVKA-II.

*Note: If the infant is not receiving vitamin supplementation at the 18 mo of age visit, no additional blood will be drawn for vitamin monitoring. If changes in the vitamin supplementation plan is required, additional testing will be done outside of the visits listed below.

Table 11. Total Amount of Blood Drawn from Infants *in the Clinical Trial (including that for the prospective observational database).*

Visit	Amount in ml drawn for research at the visit	Maximum research blood draw in ml within 2-month period	Maximum research blood draw in ml within 3-month period
Initial	4	4	4
2 weeks post op	1	5	5
4 weeks post op	8	13	13
2 months post op	1	14	14
3 months post op	8	17	22*
6 months post op	8**	8 or 13.2	13.2 or 14.2
12 months of age	13.2	13.2	13.2
18 months of age	8 or 11***	8 or 11	8 or 11
24 months of age	8	8	8
Annually from age 3	4	4	4

* This would only happen if the 3-month post-op or post-diagnosis visit was scheduled before the 3-month anniversary of the operation or diagnosis.

** When the 6 month post-op or post-diagnosis visit is at 10 months of age or greater, the blood draw at that visit will be that for 12 months of age and there will be no blood draw at 12 months of age.

***At 18 months of age, 6-9 ml of blood will be drawn to assess immunization antibody titer levels; research blood for vitamin levels, total bile acids and PIVKA-II (3 ml) will be drawn only if the infant is receiving vitamin supplementation at this visit.

The IRB guidance at the University of Michigan (site of the Data Coordinating Center) for the amount of blood that may be removed from an infant:

1. In human subjects in good health, and a hematocrit of not less than 38%, the following volumes of blood may be removed over a 3-month period, on a single occasion or in divided portions:

Body Weight (lb) - Blood Volume (ml)	
0-10	20
11-20	30
21-30	50

2. Additional volumes of blood may be removed in subsequent 3-month periods using the same criteria, as long as the subject remains in good health and maintains a hematocrit level of not less than 38 volume%.

3. If a subject may not be in good health, and in particular may have a cardiovascular, pulmonary or hematopoietic problem, the volume of blood to be removed should be reduced appropriately.

6.A5b. Side Effects

The second set of potential risks derive from reported side effects of corticosteroids, which include hypertension, hyperglycemia, hypokalemia, impaired wound healing, gastrointestinal bleeding, pancreatitis, and irritability. Despite these potential adverse events, this clinical trial is justified by the devastating nature of biliary atresia on the well-being of affected children and on the progression to end-stage liver disease in most subjects. In this context, corticosteroid treatment may result in improved bile flow, allow for better growth, and long-term survival with the native liver. To minimize potential adverse events to subjects, the investigators will monitor closely for side effects in all subjects, and promptly adhere to the action plan outlined in the Data Safety Monitoring Plan (DSMP) if side effects are identified.

Subjects will have a potential risk of adrenal insufficiency if administration of corticosteroids is suddenly discontinued after 2 weeks of treatment. This potential adverse effect will be reviewed at enrollment and at discharge from the hospital with the subject's parents or guardians. In subjects needing discontinuation of study drug/placebo for medical reasons (such as in the setting of a serious adverse event) or exit from the trial due to parent's request, a tapering and discontinuation protocol (see Section 4.F3) will be used to prevent/minimize occurrence of adrenal insufficiency.

Although fat-soluble vitamin supplementation is recommended for cholestatic infants with biliary atresia, there is a potential risk of toxicity from supplementation. Careful monitoring of vitamin concentrations/ratios is planned to reduce this risk. In addition, whenever a vitamin dose adjustment is made, follow-up testing will be performed. If there is a major or rapid change in the severity of cholestasis (e.g., rapidly decreasing serum bilirubin level), vitamin levels will be monitored more frequently.

6.A6. Alternative Treatments Considered

Corticosteroid treatment is being considered in this study as an adjuvant treatment for children with biliary atresia. At present, other adjuvant therapies may be under development, such as anti-oxidant cocktails, anti-inflammatory agents that target specific components of the immune system, and others. However, we are not aware of any studies actively enrolling subjects at this time. Preventive approaches may also become

available in the future as new discoveries are made on pathogenic agents causing biliary atresia.

6.B. Adequacy of Protection Against Risks

6.B1. Plan to protect subjects/mitigate risks

Subject confidentiality will be maintained by entering the data on the subject into a research database through a password-protected website (using SSL) maintained by the DCC. In the research database, subjects will not be identified by name, but by study numbers only. All consent documents will adhere to the HIPAA regulations, and will use the accepted terminology mandated by each site.

Careful attention to entry and exclusion criteria will also protect subjects against potential adverse effects of corticosteroid treatment. For example, screening for hyperglycemia, hypertension or infection will minimize any potential worsening of the clinical status of pre-existing diseases by corticosteroid treatment.

Blood will be drawn whenever possible at times of venipuncture for routine care or when intravenous lines are in place to reduce the risks of venipuncture. Only the blood draw at the two-week follow up visit is added by this study.

6.B2. Description of Recruitment Plan

Subjects will be recruited from subjects evaluated at, referred to, and followed at the ChiLDREN clinical centers, whom have been consented and enrolled into the ChiLDREN prospective database study and found to have biliary atresia. The investigator or study coordinator will recruit the parent(s) or guardian(s) during clinic visits or during an inpatient admission to the hospital when exploratory laparotomy and portoenterostomy are being planned for diagnosis and treatment of biliary atresia. If parent(s) or guardian(s) are not approached about the clinical trial before surgery, recruitment may also occur within 72 hours of the portoenterostomy. The investigator will discuss the study design, benefits and possible risks with the family. Printed information about the study and the consent form will be given to the family; questions about the study will be answered. The IRB-approved consent will include the purpose of the trial, the responsible parties and investigators, potential benefits, risks of participation, the right to refuse to be in the study, the right to withdraw from the study under no penalty, contact numbers and information about the responsibility for injury and payment for medical care.

6.B3. Informed Consent Process and Plan

A common template for the informed consent form will be used at each clinical site with modifications in the format as necessary to meet the requirements of the respective institutional human subjects committees. The parents/guardians will retain a copy of the signed consent form; one copy will be retained for the subject's chart and one will be included in the research records. No collection of data related to the study or to procedures will be done prior to completion of the informed consenting process.

6.B4. Assent

Assent will not be sought from study subjects because they will be infants at entry into this study.

6.C. Potential Benefits

6.C1. Description of Possible Health Benefits to Subjects

The use of corticosteroid as an adjuvant therapy following portoenterostomy has the potential to increase bile drainage and decrease hepatobiliary inflammation in infants with biliary atresia. We do not know whether improved bile drainage 6 months after portoenterostomy will lead to better long-term outcome. However, the design of this clinical trial within ChiLDREN will allow us to generate data on long-term clinical outcome by: 1) assessing clinical outcome without liver transplantation at 2 years of age, and 2) continued follow-up up to 10 years through participation of the subject in the ChiLDREN prospective database study.

Study subjects will undergo formal developmental evaluation and their parents/guardians will assess the impact of chronic liver disease on HRQOL. These evaluations have not been previously done in children with biliary atresia, and have the potential to uncover opportunities for targeted therapeutic interventions to improve neurodevelopmental outcome and HRQOL to affected children and their families. These potential benefits will extend to all subjects, regardless of their randomization to treatment or placebo groups.

There is a potential benefit of monitoring for vaccine response and identification of the need for booster immunization.

If the trial demonstrates that corticosteroid therapy does not produce positive outcomes, the data may guide the medical community at large regarding the lack of efficacy of this approach, which should discourage the incorporation of corticosteroid therapy into routine clinical care.

6.C2. Description of any incentives or rewards offered for participation

Parents or guardians of infants enrolled in the study will receive an appropriate fee per outpatient visit to reimburse them for meals and/or parking fees according to costs at each clinical site. The supplies of placebo or corticosteroid will be provided to study subjects. In addition, the clinical site research pharmacy will provide a one to two year supply of MCT-enriched infant formula for subjects that are not breastfed, prescribed doses of a liquid preparation of supplemental vitamins, and ursodeoxycholic acid. The research pharmacy will also provide monthly supplies of Ranitidine to be taken by the study subject while he/she is taking the study drug/placebo. Although part of routine clinical care of infants with biliary atresia, the cost for treatment with ursodeoxycholic acid is usually covered by the family or subject's insurance, but coverage for MCT-enriched formula and supplementation with fat-soluble vitamins is highly variable with different health insurance plans. Therefore, the provision at no cost of these items to the family will serve as an incentive to study participation, and will also help minimize variations in routine clinical care among ChiLDREN clinical sites. The clinical site research pharmacy

will also provide liquid preparation of ranitidine to be taken for 13 weeks, while the subject is taking the study drug/placebo.

6.C3 Tests Performed as Part of Research

Lab tests to evaluate side effects of the corticosteroids (e.g., glucose and electrolytes), vitamin levels, total bile acids, PIVKA-II and immunization antibody titer levels will be paid for by the research grant. The ophthalmologic examination at one year will also be paid for by the research grant.

6.D. Summary of Importance of Knowledge to be Gained from this Research

Knowledge gained from this clinical trial may directly impact the standard of medical care offered to infants with biliary atresia throughout the United States. In addition to objectively assessing whether corticosteroid therapy improves bile flow and long-term survival with native livers in an adequately powered subject population, the experimental design for this trial will also monitor for potential short- and long-term adverse effects from corticosteroids. This is especially important in view of the concerns about impaired neurodevelopmental outcome associated with corticosteroid treatment, as well as the potential incorporation of corticosteroids as part of routine care of infants with biliary atresia by the community of physicians at large. Collectively, these data will enable analysis of the risk-benefit ratio of corticosteroid treatment on clinical outcome of children with biliary atresia.

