Evaluation	Recruitment or Baseline	Diagnosis/ Surgery/ Discharge	2 wk post	1,2,3 & 6 m post Kasai	12 m age	18 m age	24 m age	At transplant
Windows for visits			±1 wk	±2wks; ±4 wks for 6 m	±1 mo	±2 mo	±2 mo	
Inf. Consent & eligibility	X							
Intake/Medical History	X		X	X	X	X	X	X
Diagnosis and surgery		X						
Discharge Assessment		X						
Medication Record	X	X	X	X	X	X	X	X
Physical Exam, Growth Measures	X	X	X	X	X	X	X	X
Blood tests -Complete blood count -LFTs, PT/INR -Electrolytes, creatinine, BUN, glucose	X	X	X	X	X	X	X	X
Blood tests -Retinol, RBP, 25OH-VitD -Vitamin E, total lipids -Bile acid, PIVKA-II				X*	X	X**	X	
Interval Medical History			X	X	X	X	X	X
Interval Sentinel Events			X	X	X	X	X	X
Neurodevelopmental Assessment (Bayley)					X		X	
Health-Related Quality of Life Inventory (HRQOL)					X		X	
Ophthalmological exam					X			
Antibody titers to vaccines						X		

*Will not be done at the 2 month follow-up, unless a dose adjustment was performed at the 4 week follow-up.

**Will be done only if infant still requires AquADEK® to maintain adequate serum levels of fat-soluble vitamins.

4.I. Surgical procedures and Laboratory Tests

Results of surgical procedure(s) and laboratory tests performed for the initial diagnosis of biliary atresia will be obtained from the medical records. These tests will include hematologic and biochemical analysis (such as complete blood count, liver function tests, prothrombin time/INR, urinalysis, etc), imaging (such as ultrasound examination and hepatobiliary scan), and results of hepatobiliary pathology. Results for tests done at the time of hospital discharge following portoenterostomy will also be obtained from the medical records. Following discharge, the following laboratory tests will be obtained in all subjects, at the time points shown in Table 6, in order to assess study outcomes: liver function tests, complete blood count, vitamin levels and prothrombin time. Serum electrolytes and glucose will also be measured to monitor for potential adverse effects of corticosteroid treatment. These laboratory tests will be performed using standard automated assays in certified clinical laboratories located at each ChiLDREN clinical center.

4.J. Preparation and Administration of Study Medication and Placebo

4.J1. Preparation, Packaging, and Labeling

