Development of infectious diseases and vaccine-preventable diseases	All emergency department visits and hospitalizations will be reported as an adverse event. If the subject is hospitalized with lower respiratory tract symptoms of unknown etiology, nasal wash will be obtained for pertussis PCR. If S. pneumoniae is isolated from the blood or a sterile body site (such as cerebrospinal fluid), isolates will be serotyped.
Development of septicemia and opportunistic infections	All events with bacteremia, fungemia, or other opportunistic infections will be reported as an adverse event.

Impaired response to childhood vaccines

Subjects will receive all routine childhood vaccines according to the schedule recommended by the American Academy of Pediatrics (AAP), with the exception of up to a 4-week delay of vaccines that would have been given during the first 4 weeks of the study drug/placebo. Vaccinations will be administered by the subject's primary care provider. At 18 months of age or at the time of liver transplantation (if younger than 18 months of age), the vaccination records of each subject will be obtained from the primary care provider for review. The number and size of doses, dates of administration, and vaccine manufacturer will be recorded. At the age of 18 months, 6-9 ml of blood will be obtained to measure serum antibody titers against individual vaccine antigens. The antibody titers will be measured by the study sites local laboratory. If a subject has received a transplant before the 18th month visit, titers should not be collected. Priority titers to be collected relate to vaccinations for Hepatitis B, Tetanus, and Polio. If serum antibody titers do not achieve protective levels as determined by the local laboratory standard and the investigator, the information will be provided to the primary care provider so that booster/re-immunization of appropriate antigen(s) is given. Absent titers will also be communicated to the primary care provider, who will treat with re-immunization as directed by the AAP guidelines for catch-up immunization.

Development of infectious diseases and vaccine-preventable diseases

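### Section 6.A5a gives 6-9 ml for a vitamin sample that Table 11 counts at 3 ml, and Table 11's 18-month row still counts 3 ml for vaccine titers that now take 6-9 ml

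*Protocol*

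**What the plan says.** Section 6.A5a of the protocol lists the research blood drawn from each infant and totals it in Table 11. Table 11 includes the repository draws itemised in Table 10. The components are:

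- **Repository draw (Table 10):** 4 ml at the initial, 4-week, 3-month, 6-month, 18-month and 24-month visits, and 9.2 ml at 12 months of age.
- **Electrolytes and glucose:** "At each follow up visit, 1 ml of blood will be drawn to monitor serum electrolytes and glucose".
- **Vitamin, bile acid and PIVKA-II sample, running text:** at 4 weeks, 3 and 6 months after surgery and at 12, 18 and 24 months of age, "6-9 ml of blood will be drawn to monitor vitamin levels, total bile acids and PIVKA-II".
- **The same sample, Table 11 footnote \*\*\* (18 months):** "research blood for vitamin levels, total bile acids and PIVKA-II (3 ml) will be drawn only if the infant is receiving vitamin supplementation".
- **Vaccine titers at 18 months, same footnote:** "6-9 ml of blood will be drawn to assess immunization antibody titer levels". Section 4.O3 agrees: "At the age of 18 months, 6-9 ml of blood will be obtained to measure serum antibody titers against individual vaccine antigens".

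For research blood per visit, Table 11 prints 8 ml at 4 weeks, 3, 6 and 24 months, 13.2 ml at 12 months, and 8 or 11 ml at 18 months. The 18-month entry is repeated in both cumulative columns. The 3-month row carries a 2-month maximum of 17 ml and a 3-month maximum of 22 ml.

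The section then cites IRB guidance under which "the following volumes of blood may be removed over a 3-month period": 20 ml for 0-10 lb, 30 ml for 11-20 lb and 50 ml for 21-30 lb. That guidance is for subjects in good health and asks for smaller volumes otherwise.

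**The concern.** There are two separate faults. The first is that one sample has two volumes within one subsection, and the larger is two to three times the smaller. The second is that the 18-month row appears not to have been updated when the titer volume became 6-9 ml, so its total does not follow from its own footnote.

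Section 6.A5 names the amount of blood as a risk of the trial, and section 6.A5a points to Tables 10 and 11 for the cumulative amount. A site that followed the sentence would draw 3-6 ml more per visit than the table discloses, from post-operative infants with liver disease. An IRB that relied on the 18-month row would see too low a total.

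**Working it through.** Let *v* be the vitamin sample and *t* the titer sample, both in ml. Repository volumes come from Table 10, and the 1 ml for electrolytes and glucose from section 6.A5a.

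**Reproducing Table 11 with *v* = 3**

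| Cell | Sum | Result | Printed |
|---|---|---|---|
| 4 weeks; 3, 6 and 24 months | 4 + 1 + 3 | 8 | 8 |
| 12 months | 9.2 + 1 + 3 | 13.2 | 13.2 |
| 2-month maximum at the 3-month visit | 8 + 1 + 8 | 17 | 17 |
| 3-month maximum at the 3-month visit | 4 + 1 + 8 + 1 + 8 | 22 | 22 |

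All match.

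**The same cells with *v* = 6 to 9**

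- 4 weeks; 3, 6 and 24 months: 5 + *v* = 11 to 14, against 8 printed.
- 12 months: 10.2 + *v* = 16.2 to 19.2, against 13.2 printed.
- 2-month maximum: (5 + *v*) + 1 + (5 + *v*) = 11 + 2*v* = 23 to 29, against 17 printed.
- 3-month maximum: 4 + 1 + (5 + *v*) + 1 + (5 + *v*) = 16 + 2*v* = 28 to 34, against 22 printed.

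None match, so the table was built on 3 ml.

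**The 18-month row**

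- Without the vitamin sample the total is 4 + 1 + *t*; with it, 4 + 1 + *t* + *v*.
- With *t* = 3 and *v* = 3: 8 and 11, exactly as printed.
- With *t* = 6 to 9 and no vitamin sample: 11 to 14. The printed 8 is 3 to 6 ml short (3/8 = 38%, 6/8 = 75%).
- With *t* = 6 to 9 and *v* = 3: 14 to 17. The printed 11 is 3 to 6 ml short (3/11 = 27%, 6/11 = 55%).

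**Another reading of 8 or 11.** The 11 could be 4 + 1 + 6, the lowest titer volume without vitamins. But the footnote makes only the vitamin sample conditional, so 8 could then not occur. Two of the three columns are also headed as maxima, and with vitamins the maximum is at least 14.

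**Against the quoted limits.** The corrected 18-month maximum, 17 ml, is below the smallest quoted figure of 20 ml. The printed 3-month maximum of 22 ml is already above 20 ml, whichever vitamin volume is meant. What the 6-9 ml reading would add is a possible excess over 30 ml: 16 + 2*v* > 30 when *v* > 7.

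**The case against.** The best defence is that the conflict shows itself. Section 6.A5a describes risk, and the vitamin-monitoring section (4.N9) sets no volume. Table 11, directly below the sentence, allows 8 ml for all research blood at most of these visits, which cannot hold 6-9 ml for vitamins plus 4 ml and 1 ml. A site would probably notice. The manuals of operations mentioned in section 5.C3 are not shown and may state the right volume. This lowers the likely harm, but the sentence is still wrong as written.

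At 18 months, the 6-9 ml for titers is disclosed in the footnote and in section 4.O3; only the sum is stale. That is fair, but the sum is what the table exists to give.

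The comparison with the IRB limits deserves little weight. The 22 ml maximum exceeds 20 ml even at 3 ml per vitamin sample, footnote \* confines it to a 3-month visit held early, and 28-34 ml arises only on a reading that is probably not intended.

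Section 4.O3 also excludes titers in children transplanted before the 18-month visit, so the corrected row covers only infants who have titers drawn. That point stands and belongs in the footnote.

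**Conclusion.** Both faults hold on the current text.

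- **Vitamin sample:** the sentence is 2 to 3 times the footnote's figure, or 3-6 ml more per visit. That 3 ml is intended is an inference, but a strong one: the five other rows with this sample and both rolling totals at the 3-month visit fit 3 ml and nothing in the 6-9 ml range.
- **18-month row:** understated by 3-6 ml in all three columns. The corrected figures assume the Table 10 repository draw, the 1 ml safety draw, 6-9 ml for titers and 3 ml for vitamins.

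At 18 months the consequence is under-disclosure, not a passed limit. What sites actually drew, and what the consent form said, cannot be judged from the protocol. No endpoint, sample size or efficacy analysis is affected. It should be fixed because it concerns blood volumes in sick infants and the correction is exact.

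**What to change.** 1. In section 6.A5a, change 6-9 ml to 3 ml in the sentence on the vitamin, bile acid and PIVKA-II sample.
2. In Table 11, change the 18-month row in the visit column and both cumulative columns to 11-14 ml without the vitamin sample and 14-17 ml with it. Note that this applies to infants who have titers drawn.
3. Check the IRB submission and consent figures against the corrected values.

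If 6-9 ml is really intended for the vitamin sample, correct footnote \*\*\* and every affected row instead. The 3-month maximum would then be 28-34 ml and would need justifying against the quoted 20 and 30 ml.

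Two things are worth settling while the table is open, though neither is shown here to be an error. One is to recheck the 6-month cumulative cells, which were not rederived. The other is to say whether a 2-month vitamin retest is counted. The Table 6 footnote on the vitamin tests reads "Will not be done at the 2 month follow-up, unless a dose adjustment was performed at the 4 week follow-up", while the note above Table 11 says "If changes in the vitamin supplementation plan is required, additional testing will be done outside of the visits listed below".

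The cost is one sentence and three table cells, a consistency check of the consent form, and notice to the IRBs.
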